8. STUDY EVALUATIONS

For the timing of efficacy and quality of life assessments during the study, refer to the study schedule in section 7.1 and 7.2.

8.1 Efficacy Endpoints and Evaluations

8.1.1 *Primary Efficacy Endpoint and Evaluations*

- Global assessment of spasticity – Modified Ashworth scale will be used for efficacy evaluation.

8.1.2 *Secondary Efficacy Endpoints and Evaluations*

- Patient's Quality of Life (QOL) evaluation – standard DAS scale will be used for QOL evaluation. Based on the subject interview, the investigator will fulfil the DAS QOL questionnaire, due to the absence of translated Czech version of the DAS.

- Interval between separate administration sessions – interval between current and previous injection visit will be described.

8.2 Safety Endpoints and Evaluations

8.2.1 Related Adverse Events

Treatment related AEs will be collected from the first treatment administration to the end of the Study. RAEs will be elicited by spontaneous reports. Due to the non-interventional character of the study, no pro-active safety data collection should take place and only spontaneously mentioned safety events should be reported. Further details for RAE reporting can be found in Section 10.

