7.2 Study Visits

7.2.1 Baseline (Day 1, visit V1)

All subjects attending the centre for their normal Dysport treatment will receive Dysport as decided by the treating physician, in accordance with the SmPC. The following details will be recorded on the Study CRF:

- Centre number, Subject number, Subject initials
- Demography
- Significant medical or surgical history
- Prior and concomitant medication
- Previous medication for stroke
- Stroke details
- Modified Ashworth scale, DAS scale
- Dysport administration (location, dosage)
- Related Adverse Events (at this visit injection related AEs only)

7.2.2 *Follow-up visits (V2, V3, V4, V5)*

At the subject's scheduled return to the center (Visit 2, the date depends on investigator's judgement, it is usually about 4 weeks later), the investigator will make routine control of treatment efficacy (V2). During this visit, both Modified Ashworth and DAS scales are evaluated according to routine practice. Treating physician will also perform an assessment of safety, and details on any treatment related adverse events will be collected.

After fadeaway of Dysport effect, subject will come to next injection visits (V3, V4,) within which Dysport will be injected again according to investigator decision. Treatment interval will be counted (V3 - V1, V4 - V3).

Visit V5 will be performed by telephone contact and is also the End of study visit.

During visit 5, which will take place within 3-5 weeks following last injection, subjects will be contacted by telephone to discuss any treatment related Adverse events (RAEs) that they have had since their treatment and Modified Asworth and DAS scale.

Collection of treatment related adverse events, if any, will be made during V1, V2, V3, V4 and V5.

7.2.3 *Study Completion or Withdrawal*

Study is completed if current visits exceed 1 year from visit 1 or when the Dysport treatment is finished/withdrawn

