10.2 Recording and Follow-up of related adverse events

At each visit the subject should be asked a non-leading question such as: "Do you feel different in any way since starting the new treatment/the last assessment?"

All AEs related to survey medication will be recorded on the RAE page(s) of the CRF. Related Events involving drug reactions, accidents, illnesses with onset during the treatment phase of the survey, or exacerbation's of pre-existing illnesses should be recorded.

RAEs already recorded and designated as 'continuing' should be reviewed at each subsequent assessment.

For all registered RAEs, the Investigator must pursue and obtain information adequate both to determine the outcome of the RAE and to assess whether it meets the criteria for classification as a RSAE requiring immediate notification to the Sponsor or its designated representative. The Investigator is required to assess causality and record that assessment on the CRF. Follow-up of the RAE, after the date of therapy discontinuation, is required if the RAE or its sequel persist. Follow-up is required until the event or its sequel resolve or stabilise at a level acceptable to the Investigator and the Sponsor's clinical monitor or his/her designated representative.

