11.4 Statistical/Analytical Methods

Statistical analyses will be performed / managed by CRO.

A Reporting and Analysis plan (RAP) describing the planned statistical analysis in detail with tables, figures and listings (TFLs) templates will be developed as a separate document.

11.4.1 *Demographic and Other Baseline Characteristics*

Descriptive summary statistics (n, mean, standard deviation (SD), median, minimum, maximum) of demographic and treatment dosage/interval will be presented.

11.4.2 *Subject Disposition and Withdrawals*

The numbers of subjects who were treated, discontinued and completed at each of the Study periods will be tabulated. Primary reasons for discontinuation of Study treatment will be tabulated.

11.4.3 *Pharmacokinetic Data*

N/A

11.4.4 *Efficacy Evaluation*

Descriptive analyses will be provided using Modified Ashworth scale and DAS scale at each visit and describing also changes from visit 1.

11.4.5 *Safety Evaluation*

All safety data will be included in the subject data listings. Analyses and summary tables will be based upon the safety population.

RAEs will be coded according to the Medical Dictionary for Regulatory Activities (MedDRA) and will be classified by MedDRA preferred term and system organ class. RAE listings will be presented by subject, system organ class and preferred term.

Incidence of all reported RAEs/treatment emergent related AEs (TERAE) and SRAEs will be tabulated. In addition, summary tables will be presented by maximum intensity, drug relationship and RAEs/TERAEs associated with premature withdrawal of survey medication.

A TERAE is defined as any RAE that occurs during the active phase of the survey if:

- it was not present prior to receiving the first dose of Survey medication, or
- it was present prior to receiving the first dose of Survey medication but the intensity increased during the active phase of the survey, or
- it was present prior to receiving the first dose of Survey medication, the intensity is the same but the drug relationship became related during the active phase of the survey.

Treatment emergent RAEs will be flagged (*) in the RAEs listings.

Concomitant medication will be coded by using WHO Drug Dictionary and will be summarised with the number and percentage of subjects receiving concomitant medication by drug class and preferred drug name.

11.5 *Subgroup Analyses*

N/A

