13.3 Source Data Verification

As required by GCP, the Sponsor assigned monitor must verify, by direct reference to the source documents, that the data required by the protocol are accurately reported on the CRF.

The source documents must, as a minimum, contain the following; a statement that the subject is included in a clinical Study, the identity of the Study, the date that informed consent was obtained prior to participation in the study, diagnosis and eligibility criteria, visit dates (with subject status), Study medication administration, and spontaneously reported AEs and associated concomitant medication.

Definition for source data and source documents are given below:

- **Source Data:** All original records and certified copies of original records of clinical findings, observations, or other activities necessary for the reconstruction and evaluation of the trial. Source data are contained in source documents (original records or certified copies). [ICH GCP Section 1.51]
- **Source Documents:** Original documents, data and records (e.g. hospital records, clinical and office charts, laboratory notes, memoranda, subjects' diaries or evaluation checklists, pharmacy dispensing records, recorded data from automated instruments, copies or transcriptions certified after verification as being accurate copies, microfiches, photographic negatives, microfilm or magnetic media, x-rays, subject files, and records kept at the pharmacy, at the laboratories and at medico-technical departments involved in the clinical trial). [ICH GCP Section 1.52]

The items recorded directly on the CRF and considered as source data will be described at each site in a site specific document signed by the investigator and filed in the investigator file.

The subject must have consented to their medical records being viewed by Sponsor-authorized personnel, and by local, and possibly foreign, CAs. This information is included in the informed consent.

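### Section 8.2.1 limits adverse event collection to spontaneous mention, while 10.2 and the V5 call in 7.2.2 have subjects asked, and nothing says which prevails, so the pooled RAE incidence may mix two ascertainment methods.

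*Protocol*

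**What the plan says.** Section 8.2.1 sets the rule for the only safety endpoint, treatment-related adverse events. It states "RAEs will be elicited by spontaneous reports" and then, giving the non-interventional character of the study as the reason, that "no pro-active safety data collection should take place and only spontaneously mentioned safety events should be reported". It closes with "Further details for RAE reporting can be found in Section 10".

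Section 10.2, to which the reader is thus sent, begins "At each visit the subject should be asked a non-leading question such as" and supplies a sample question on whether the subject feels different since starting treatment or since the last assessment.

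Section 7.2.2 says of V2: "Treating physician will also perform an assessment of safety, and details on any treatment related adverse events will be collected". Of V5 it says that "subjects will be contacted by telephone to discuss any treatment related Adverse events (RAEs) that they have had since their treatment"; the same call also covers the Modified Ashworth and DAS scales. Table 1 marks RAEs at all five contacts, and Section 7.2.1 limits V1 to injection-related events.

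Section 13.3 lists, among the minimum contents of the source documents, "spontaneously reported AEs and associated concomitant medication".

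Section 11.4.5 plans the output: "Incidence of all reported RAEs/treatment emergent related AEs (TERAE) and SRAEs will be tabulated".

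**The concern.** Whether subjects are asked about adverse events, or only those who volunteer something are recorded, is part of what an adverse event frequency means. The protocol gives both instructions. A centre that works from 8.2.1 has good reason not to ask, since that section says why asking is out of place. A centre that works from 10.2 will ask at every visit. The V5 call raises the subject of RAEs in either case.

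About 200 subjects are to come from approximately 10-30 centres (Section 6.1). The primary objective is risk/benefit, and the RAE tables are the safety half of it. If practice differs between centres, the pooled numerator is a mixture in unknown proportions. The protocol nowhere asks for a record of how a report arose, so no later analysis could split the mixture. An analysis plan cannot repair this either, because it is a matter of conduct at the sites.

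**Working it through.** The protocol states no expected RAE rate, so there is no figure to reproduce. The check is a comparison of the text, followed by an illustration.

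**Step 1: classify each instruction.**

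| Section | Instruction | Method |
|---|---|---|
| 8.2.1 | spontaneous mention only; no pro-active collection | spontaneous |
| 13.3 | source documents hold spontaneous reports | spontaneous |
| 10.2 | open question to the subject at each visit | solicited |
| 7.2.2, V5 | call placed to discuss RAEs | solicited |
| 7.2.2, V2 | physician assesses safety, RAE details collected | fits either |
| 7.2.1, V1 | injection-related events only | fits either |

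The conflict is therefore 8.2.1 and 13.3 against 10.2 and the V5 text.

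**Step 2: look for a precedence rule.** The only link is the pointer from 8.2.1 to Section 10. It promises further detail and does not say that Section 10 overrides the restriction. Following it leads to the opposing instruction.

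**Step 3: follow the data to the table.** Section 11.4.5 tabulates all reported RAEs in one pooled safety population. Its planned breakdowns are by maximum intensity, drug relationship and association with premature withdrawal, none of which separates solicited from spontaneous reports.

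**Step 4: illustrate the effect.** Inputs: N = 200 (Sections 6.1 and 11.3). All else is assumed: p, the incidence when subjects are asked; r, the fraction of p still captured when they are not asked; f, the share of subjects who are asked.

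Expected tabulated incidence = f × p + (1 − f) × p × r

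With p = 10% and r = 0.5:

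- f = 0: 0.10 × 0.5 = 5.0%, or 10 subjects
- f = 0.5: 0.5 × 0.10 + 0.5 × 0.10 × 0.5 = 7.5%, or 15 subjects
- f = 1: 0.10 = 10.0%, or 20 subjects

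Over p from 5% to 20% and r from 0.3 to 0.8:

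- nobody asked: 0.05 × 0.3 = 1.5% (3 subjects) to 0.20 × 0.8 = 16% (32 subjects)
- everybody asked: 5% (10 subjects) to 20% (40 subjects)
- ratio at a given p: 1/r, from 1/0.8 = 1.25 to 1/0.3 = 3.3

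With r = 1 there is no difference. The f = 0 case also supposes that the V5 call prompts nothing, which is not how 7.2.2 describes it.

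**The case against.** The best defence is that an open, non-leading question names no event, so what the subject then says can still be called spontaneous. Section 8.2.1 refers to Section 10 for detail, so a site could take 10.2 as the way spontaneous mention is obtained. This has some force for V2 to V4. It does not remove the conflict, because 8.2.1 does more than bar leading questions: it rules out pro-active collection. A question put to every subject at every visit is pro-active, and a call made to discuss RAEs is more plainly so.

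A second defence is the modest aim of the study. Section 11.3 says that it is not meant to support definitive conclusions on safety or efficacy, Section 11.3.1 excludes testing, and there is no comparator, so no between-arm bias can arise. This stands and limits the consequence. It does not remove it, since a descriptive frequency still needs a defined method of collection.

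Three stronger readings are tempting but not supported:

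- A reader might infer that one section forbids what another requires. Both use *should*, so these are opposed instructions rather than a strict prohibition and a strict duty.
- A reader might infer that the wording alone doubles the RAE rate. Any such ratio only restates the capture fractions assumed, and the protocol gives none.
- A reader might infer that centre or visit comparisons would be distorted. No such comparison of RAEs is planned, and Section 11.5 lists subgroup analyses as not applicable.

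**Conclusion.** The inconsistency is real and stands on the protocol's own text. Sections 8.2.1 and 13.3 describe spontaneous-only collection, 10.2 and the V5 call in 7.2.2 describe asking, and no rule settles the matter. If centres resolve it differently, the incidence in 11.4.5 will be a mixture that cannot be taken apart afterwards.

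The likely direction is more reports where subjects are asked, which is a reasonable inference and not a statement of the protocol. The size is unknown: the figures in the working rest wholly on assumed rates and range from no difference to about three-fold between the two extremes, with mixed practice lying between. The consequence is confined to the interpretation of a descriptive safety table. It still warrants correction before data are collected, because the table is the study's main safety output and the remedy is cheap.

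**What to change.** State one ascertainment method for all centres and align Sections 7.2.2, 8.2.1, 10.2 and 13.3 with it. The method must also agree with Section 4.3, which says that no safety measures beyond normal practice are collected, and with the V1 limit to injection-related events. Either route will do:

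- **(a) Ask everyone.** Keep the open question of 10.2 at the follow-up contacts V2 to V5, and narrow its timing to those contacts so that V1 stays as 7.2.1 has it. Remove the spontaneous-only and no pro-active sentences from 8.2.1 and the word *spontaneously* from 13.3. State in 4.3 that the question is part of routine follow-up; otherwise the contradiction merely moves there.
- **(b) Ask no one.** Keep 8.2.1 and 13.3, delete the question from 10.2, and reword the V5 enquiry in 7.2.2 and the V5 entry in Table 1 so that the call only records events the subject mentions unprompted. Label the 11.4.5 tables as the frequency of spontaneously reported RAEs.

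Under either route, state the method beside the tables in the report.

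The cost is a wording amendment and a letter to sites, with no added visit. If the change is judged substantial under Section 15, as affecting scientific value or conduct, documented ethics committee approval is needed before it takes effect. Route (a) may raise the reported RAE rate.

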9. STUDY TREATMENTS

9.1 Study Treatments Administered

Administration of Dysport will be supervised by the Investigator.

Study medication

Chemical name:	Clostridium botulinum type A toxin-hemagglutinin complex
Study Code:	Dysport
Dosage form:	Inj. sicc.
Strength:	500 units / vial
Manufacturer:	Ipsen Biopharm Ltd., Wrexham, United Kingdom (UK)
Description:	Dysport is supplied as a white, lyophilized powder containing 500 units of Clostridium botulinum type A toxin-haemagglutinin complex, 125 µg human serum albumin, and 2.5 mg of lactose. The product will be reconstituted at the investigational sites with sterile physiologic saline solution for injection without preservative.

9.2 Subject Identification and Allocation to Study Treatment

All subjects enrolled must be identifiable throughout the Study. The Investigator will maintain a list of subject numbers and names at the Study center to enable records to be found at a later date if required.

The subject number will be allocated at baseline visit following the chronological order of the subject entry into the Study at a particular site. Subjects will be identified using a unique subject identification during the Study: site number + subject number. Subject number and site number will be noted in the CRF.

9.3 Study Treatment Supply

The centre will prescribe Dysport, each bearing a unique batch number, by their normal method. The Dysport is the commercially available medicine in the Czech Republic.

Centres will prescribe Dysport according to their normal practice and in respect to the SmPC.

9.4 Compliance

N/A

9.5 Study Treatment Storage

Until dispensed to the subjects, Dysport will be stored refrigerated under storage conditions mentioned in SmPC, as is the custom at the hospital/practice.

9.6 Concomitant Medication/Therapy

N/A

10. RELATED ADVERSE EVENT REPORTING

Only related to survey medication AEs will be registered during this survey.

An RAE is the development of an undesirable medical condition or the deterioration of a pre-existing medical condition following or during exposure to a pharmaceutical product, considered causally related to the product. An undesirable medical condition can be symptoms (e.g. nausea, chest pain), signs (e.g. tachycardia, enlarged liver) or the abnormal results of an investigation (e.g. laboratory findings, electrocardiogram). In clinical studies an RAE can include an undesirable medical condition occurring at any time, including run-in or washout periods, even if no survey treatment has been administered.

This definition includes events occurring from the time of the subject receiving the first administration of Dysport until the end of the Study.

10.1 Categorisation of Related Adverse Events

10.1.1 Intensity Classification

RAEs will be classified as mild, moderate or severe according to the following criteria:

- | | |
|-----------|---|
| Mild: | symptoms do not alter the subject's normal functioning |
| Moderate: | symptoms produce some degree of impairment to function, but are not hazardous, uncomfortable or embarrassing to the subject |
| Severe: | symptoms definitely hazardous to well-being, significant impairment of function or incapacitation. |

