11.3.1 Significance Testing and Estimations

As this is a descriptive (efficacy/safety and tolerability) Study, no statistical testing will be carried out.

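### The three intensity grades in Section 10.1.1 are neither exhaustive nor mutually exclusive, so some related adverse events must be graded at the investigator's discretion

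*Protocol*

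**What the plan says.** Section 10.1.1 fixes the scale: "RAEs will be classified as mild, moderate or severe according to the following criteria". The definitions, starting with the one that matters most here, are these:

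- The middle grade is described by the phrase "symptoms produce some degree of impairment to function, but are not hazardous, uncomfortable or embarrassing to the subject".
- The lowest grade looks at function alone and applies where "symptoms do not alter the subject's normal functioning".
- The highest grade can be reached by any one of three routes, given as "symptoms definitely hazardous to well-being, significant impairment of function or incapacitation".

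No other section supplies a fourth grade, a tie-break or an alternative definition. Section 11.4.5 then uses the grade in reporting: "summary tables will be presented by maximum intensity, drug relationship and RAEs/TERAEs associated with premature withdrawal of survey medication". RAEs are the only safety endpoint (Section 4.2.2), and risk/benefit is the primary objective (Section 3.1).

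**The concern.** The grades are plainly meant to rise with loss of function, from none through some to significant. The moderate line adds a second condition that cuts across that order, because it requires the symptoms to be free of discomfort and embarrassment. Mild and severe do not mention either. Some impairment with some discomfort is an ordinary presentation for a symptomatic reaction (Section 10 itself gives nausea and chest pain as examples of symptoms), yet the text excludes it from the grade where one would expect it.

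Hazard is handled unevenly too. Mild does not mention it, moderate requires its absence, and severe requires it to be definite.

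An investigator who meets one of these cases has to depart from the written definition or choose between two that both apply. The grade is assigned when the event is recorded, so a later analysis plan cannot repair it: neither discomfort nor degree of impairment can be recovered from a recorded grade. At stake is whether a given grade means the same thing in every centre when RAEs are tabulated by maximum intensity.

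**Working it through.** The plan states no figure to reproduce, and no power or error-rate calculation applies. The check is a truth table built from the definitions in Section 10.1.1.

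**Inputs**

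- Mild = function unaltered.
- Moderate = some impairment AND not hazardous AND not uncomfortable AND not embarrassing.
- Severe = definitely hazardous OR significant impairment OR incapacitation.

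**Step 1: hazard taken as none or definite.** Function (unaltered / some impairment / significant impairment or incapacitation) × hazard (none / definite) × uncomfortable or embarrassing (no / yes) gives 3 × 2 × 2 = 12 combinations.

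| Function | Hazard | Not uncomfortable | Uncomfortable or embarrassing |
|---|---|---|---|
| Unaltered | None | Mild | Mild |
| Unaltered | Definite | Mild and severe | Mild and severe |
| Some impairment | None | Moderate | **No grade** |
| Some impairment | Definite | Severe | Severe |
| Significant | None | Severe | Severe |
| Significant | Definite | Severe | Severe |

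Totals: 2 mild only + 1 moderate + 6 severe only + 2 both mild and severe + 1 with no grade = 12.

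**Step 2: hazard taken as none, possible or definite.** This level is needed because moderate excludes hazard while severe asks for definite hazard. It gives 3 × 3 × 2 = 18 combinations, adding 6 rows to Step 1:

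- Unaltered function, possible hazard: mild (2 combinations).
- Some impairment, possible hazard: not mild, not moderate, not severe (2 combinations, no grade).
- Significant impairment, possible hazard: severe (2 combinations).

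Totals: 4 mild only + 1 moderate + 8 severe only + 2 both + 3 with no grade = 18.

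**Step 3: what uses the grade.** The RAE table by maximum intensity (Section 11.4.5) does. Overall RAE incidence, serious RAE incidence and RAEs associated with withdrawal do not. Immediate reporting depends on the seriousness criteria in Section 10.3.1, and the discontinuation text in Section 10.6 does not mention intensity.

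**Step 4: spread of raters.** Section 6.1 plans about 200 subjects in 10 to 30 centres, that is 200/30 ≈ 7 to 200/10 = 20 subjects per centre. Many investigators would each settle the ungraded case on their own reading.

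**The case against.** The strongest reply is that the scale is really a scale of function. Some impairment appears only under moderate, so an investigator who must pick one of three boxes has an obvious match and may well ignore the stray words about discomfort. The study is also single-arm and descriptive: Section 11.3.1 says that "no statistical testing will be carried out", and Section 11.3 disclaims definitive conclusions about safety. No comparison is biased, and only one descriptive split is touched.

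Much of this stands, and it limits the consequence. It does not remove the fault. A rule that gives a sensible answer only when part of it is ignored leaves each rater to decide whether to ignore it, and in a descriptive study the tables are the result.

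Three stronger readings are tempting, and the protocol does not support them.

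- *That such events will move to mild or severe, making the table unreliable.* Nothing shows this. Either move would contradict the function wording as directly as keeping the event at moderate contradicts the discomfort wording, and many raters may simply keep it at moderate.
- *That a large share of moderate events is affected.* The protocol gives no frequency of discomfort among RAEs. Any percentage would only repeat the assumption put in.
- *That treatment-emergent status is also compromised.* Section 11.4.5 does use intensity where "it was present prior to receiving the first dose of Survey medication but the intensity increased during the active phase of the survey". But RAEs are collected from the first administration onward (Section 8.2.1), and the V1 items in Section 7.2.1 include no intensity grade for pre-dose conditions. That route is marginal, and its weakness comes mainly from the missing pre-dose grade.

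**Conclusion.** The point holds as a defect of definition. As written, the three grades leave 1 of 12 combinations without a grade and give 2 of 12 two grades; if possible hazard is recognised as a separate level, 3 of 18 have no grade. The main gap is the non-hazardous event with some impairment and some discomfort.

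The effect is confined to the mild/moderate/severe split in the maximum-intensity table, which depends to an unknown extent on how each investigator resolves these cases. The combinations are logical cases and are not equally likely, so the counts say nothing about how many events are affected. The conclusion rests on reading the definitions literally and on no clarification existing elsewhere. The protocol contains none; the CRF and its guidance are not shown and might contain one. Correction is worthwhile because the wording is wrong and cheap to repair, not because a distortion has been demonstrated.

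**What to change.** Reword Section 10.1.1 so that the grades are ordered, exhaustive and exclusive, for example:

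- Mild: normal functioning is unaltered and the event is not definitely hazardous.
- Moderate: function is impaired to some degree; the event may be uncomfortable or embarrassing but is not definitely hazardous.
- Severe: the event is definitely hazardous to well-being, or impairs function significantly, or incapacitates.
- An event that meets more than one definition takes the highest grade.

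The qualifier *definitely* is needed in the mild line as well as the moderate one. If mild merely required absence of hazard, a possibly hazardous event with unaltered function would become ungraded.

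Checked against the 18 combinations: mild takes 1 × 2 × 2 = 4 (unaltered function, hazard none or possible, either discomfort level). Moderate takes 1 × 2 × 2 = 4 (some impairment, same hazard and discomfort levels). Severe takes 3 × 1 × 2 = 6 with definite hazard plus 1 × 2 × 2 = 4 with significant impairment and no definite hazard. The total is 4 + 4 + 10 = 18, each graded once.

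Use the same text wherever the CRF gives the intensity definitions. The cost is a short wording change in the protocol and, if it repeats the definitions, the CRF. No data item, visit or analysis is added.
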